#### 5.5.1.5.2 Laboratory values over time

Laboratory data (clinical chemistry, hematology, urinalysis and other screening test) and changes from Baseline (if applicable) for numeric variables will be listed for SS and time point. Any laboratory measurements that are BLQ or ALQ will be handled as described in [Section 5.5.1.5.1](#). Values outside the reference range for the numeric variables will be flagged in the listings. The reference ranges will also be reported in the listings.

Chemistry and hematology parameters will be summarized on the SS at each time point, for both absolute values and changes from Baseline.

Laboratory variables will be grouped according to the laboratory function panel and categorized as normal, high or low, if applicable, based on the reference range supplied by the analytical laboratory.

Liver function test elevations should be listed. Potential Hy's Law is defined as a participant with (AST or ALT > 3 x ULN) and TBL > 2 x ULN and ALP < 2 x ULN on the same visit.

In order to meet the above criteria, a participant must experience the elevation in bilirubin and ALT or AST at the same visit. For example, a participant who experiences a  $\geq 2$  x ULN elevation of bilirubin at one visit and a 3 x ULN elevation in ALT (or AST) at a subsequent visit has not fulfilled the Hy's law criteria.

Markedly abnormal laboratory values will generally be defined as those categorized as Grade 3 or higher based on the Rheumatology Common Toxicity Criteria (RCTC) v2.1 (Woodworth et al, 2007). Definitions of markedly abnormal values using the Grade 3 cutpoints are given in the tables below ([Table 5-3](#) for markedly abnormal hematology values and [Table 5-4](#) for markedly abnormal biochemistry values). Any ambiguity about the RCTC criteria was resolved by correspondence with the senior author. In particular, the published Grade 3 cutpoint for lymphocytes (<1.0) was found to be too high, corresponding with the lower limit of normal, and thus was changed to <0.5.

Markedly abnormal laboratory (hematology and biochemistry) values with abnormality flag and Hy's Law will be flagged in laboratory listing together for SS and each time point.

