8.3.6 Adverse events of special interest

An AE of special interest is any AE that a regulatory authority has mandated be reported on an expedited basis, regardless of the seriousness, expectedness, or relatedness of the AE to the administration of a UCB product/compound. For CZP, the following events require immediate reporting (within 24 hours regardless of seriousness) to UCB:

- Hy's Law
 - Potential Hy's Law, defined as $\geq 3 \times \text{ULN}$ ALT or AST with coexisting $\geq 2 \times \text{ULN}$ total bilirubin in the absence of $\geq 2 \times \text{ULN}$ ALP, with no alternative explanation for the biochemical abnormality (ie, without waiting for any additional etiologic investigations to have been concluded). Follow-up information should be reported if an alternative etiology is identified during investigation and monitoring of the participant.
- Serious infections, including opportunistic infections.
- Malignancies, including lymphoma.
- Congestive heart failure.
- Demyelinating-like disorders.

- Aplastic anemia, pancytopenia, thrombocytopenia, neutropenia, and leukopenia.
- Serious bleeding events.
- Lupus and lupus-like syndrome.
- Serious skin reactions (eg, Stevens-Johnson syndrome, toxic epidermal necrosis, and erythema multiforme).

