### 6.1.3 Medical history

Medical history will be listed and summarized for the SS and will include the MedDRA version 23.1 system organ class (SOC) and preferred term (PT). Procedure history will be listed separately from the medical history including date of procedure and relationship with RA based on the SS. Similarly, concomitant medical procedure will be also listed separately including date of procedure and procedure primarily relationship based on the SS. For study participants with DILI events, hepatic events supplemental medical history and relevant data (potentially hepato-toxic medication, symptoms of hepatitis and symptoms of hypersensitivity) for study participants with suspected DILI event will be listed with liver function laboratory results.

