### 6.1.7 AEs of Special Interest (AESIs)

An AE of special interest is defined as following events:

- Hy’s Law (as described in [Section 5.5.1.5.2](#))
- Serious infections, including opportunistic infections.
- Malignancies, including lymphoma.
- Serious cardiovascular events - also called Major Adverse Cardiac Events (MACE)
- Congestive heart failure.
- Demyelinating-like disorders.
- Aplastic anemia, pancytopenia, thrombocytopenia, neutropenia, and leukopenia.
- Serious bleeding events.
- Lupus and lupus-like syndrome.
- Serious skin reactions (eg, Stevens-Johnson syndrome, toxic epidermal necrosis, and erythema multiforme).

Subsets on Adverse Events of Special Interest (AESIs) will either be extracted via Structured MedDRA Query (SMQ), via other automated queries based on search criteria specified by UCB or via manual medical review from the set of TEAEs or serious TEAEs.

Some types of AESIs are identified manually. For those, textual reporting in the CSR is deemed sufficient and no additional summary tables need to be generated. For others, especially those with automated search criteria additional TEAE summary tables are planned.

All manual searches and reviews have to be occurred prior to data cleaning meeting(DCM) and data evaluation meeting (DEM). A final review after database lock will be also executed in the framework of the data cleaning and data evaluation meeting.

The MedDRA SMQ terms are based on MedDRA version 23.1. In case that later MedDRA versions will be used, the appropriateness and spelling of the terms need to be reviewed and adapted accordingly.

The following summary tables will be produced for AESIs:

- TEAEs by SOC, HLT and PT for AESIs along with number and percentage summary
- Serious TEAEs by SOC, HLT and PT for AESI along with number and percentage summary

All AESIs the term(s) for extraction are specified in Table 6–1:

PUBLIC COPY  
This document cannot be used to support any marketing authorization application and any extensions or variations thereof.

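### The SAP's potential Hy's Law rule uses strict limits (>3 x and >2 x ULN) where Protocol 8.3.6 uses inclusive ones (≥3 x and ≥2 x ULN), so cases exactly on a limit are not flagged

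*SAP*

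**What the plan says.** SAP 5.5.1.5.2 calls a participant a potential Hy's Law case when the values meet "AST or ALT > 3 x ULN) and TBL > 2 x ULN and ALP < 2 x ULN on the same visit". The same section says that markedly abnormal values and Hy's "Law will be flagged in laboratory listing together for SS and each time point".

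SAP 6.1.7 puts Hy's "Law (as described in" Section 5.5.1.5.2) first in its list of AESIs. It then says "All AESIs the term(s) for extraction are specified in" Table 6–1, but that AESI table has no Hy's Law row. The sentence in 5.5.1.5.2 is therefore the only Hy's Law rule in the SAP.

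Protocol 8.3.6 sets the AESI at ≥3 x ULN "ALT or AST with coexisting" ≥2 x ULN total bilirubin, provided ALP is not ≥2 x ULN and "with no alternative explanation for the biochemical abnormality". Such a case must reach the sponsor within 24 hours. SAP 6.2, which should record changes to protocol-planned analyses, is marked not applicable.

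**The concern.** Two documents for the same trial define the same safety event with different cut-points, and nothing says that the change was intended. The SAP rule is the narrower of the two, so any disagreement goes one way: a case that the protocol counts is not labelled in the study outputs. An event reported to the sponsor as potential Hy's Law could then appear in the laboratory listing without that label. Read literally, SAP 6.1.7 would also leave it without the Hy's Law AESI flag in the AE listings, unless medical review added it.

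The rest of the text suggests a slip. The example that follows the definition in SAP 5.5.1.5.2 uses ≥2 x ULN for bilirubin and 3 x ULN for the transaminase. SAP Table 5–4 also marks total bilirubin from 2 x ULN inclusive. The liver rules in Protocol Appendix 2 and Appendix 6 use ALT ≥3 x ULN and bilirubin ≥2 x ULN.

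**Working it through.** The plan gives no figure to reproduce. The check compares the two rules at their limits and then asks how often a tie could occur.

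**Rules**, with T the higher of AST and ALT, B total bilirubin and P ALP, all in multiples of ULN at one visit:

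- Protocol 8.3.6: T ≥ 3 and B ≥ 2 and not (P ≥ 2). The last condition is the same as P < 2.
- SAP 5.5.1.5.2: T > 3 and B > 2 and P < 2.

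The protocol's clause on alternative explanations is a clinical judgement and is left out of the comparison.

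**Boundary comparison.** Each quantity was set just below, at and just above its limit: T at 2.99, 3, 3.01; B and P at 1.99, 2, 2.01. This gives 3 x 3 x 3 = 27 combinations. The rules disagree in 3, all with P = 1.99. With P < 2, the combinations at or above the protocol limits are:

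| T | B | Protocol | SAP |
|---|---|---|---|
| = 3 | = 2 | yes | no |
| = 3 | > 2 | yes | no |
| > 3 | = 2 | yes | no |
| > 3 | > 2 | yes | yes |

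The protocol counts 4 and the SAP counts 1, so 3 of 4 differ, and each of those 3 contains an exact tie. This counts logical cells and is not a probability, because the fourth cell holds every qualifying case that is not a tie. The SAP never flags a case that the protocol rule misses. With ≥ in both places the two rules are logically identical and no combination differs.

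**Opportunities for a case.**

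- Screening: none among eligible participants. Protocol Exclusion Criterion 13 bars total bilirubin above ULN, or above 1.5 x ULN with Gilbert's syndrome, and both are below 2 x ULN.
- After Baseline: safety laboratory tests are scheduled at Week 12 and at the Safety Follow-up (SFU) Visit. With 30 participants completing both, that is 2 x 30 = 60 participant-visits.
- This is not a strict ceiling. A separate Early Discontinuation Visit as well as SFU after Week 12 for every participant would give 3 x 30 = 90, and replacements or unscheduled tests could add more. The Schedule of Activities shows one combined SFU/EDV column, so about 60 is the realistic scheduled figure.

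**How narrow a tie is.** The documents give neither reporting units nor ULN values, so these are assumptions.

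- ALT in whole U/L. ULN 35: values from 3 x to 4 x ULN run from 105 to 140, which is 140 − 105 + 1 = 36 values. ULN 50: 150 to 200, which is 51 values. One value in each band is the tie, so 1 of 36 to 1 of 51.
- Bilirubin in steps of 0.1 mg/dL. ULN 1.0: values from 2 x to 3 x ULN run from 2.0 to 3.0, which is 11 values. ULN 1.3: 2.6 to 3.9, which is 14 values. So 1 of 11 to 1 of 14.

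These are shares of reportable values, not probabilities, and they matter only once a participant is already in the Hy's Law range.

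**The case against.** The strongest reply is that the mismatch has almost no practical effect.

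- All three disputed combinations have bilirubin at or above 2 x ULN, which Table 5–4 marks as markedly abnormal, and those marks appear in the same listing as the Hy's Law flag. A reader of the listing would see the bilirubin highlighted. A transaminase at exactly 3 x ULN would not be marked by Table 5–4, which uses >3 x ULN, but would still be flagged as outside the reference range.
- SAP 5.5.1.5.2 adds "Liver function test elevations should be listed", and SAP 6.1.3 says that relevant data "for study participants with suspected DILI event will be listed with liver function laboratory results".
- Investigator reporting and the stopping criteria follow the protocol's inclusive limits. Protocol Appendix 3 gives potential Hy's law as an example of an important medical event that should usually be considered serious. SAP 6.1.7 also allows AESI subsets to be found by manual medical review.
- The protocol does not have a single Hy's Law rule. Appendix 2 and Appendix 6 use ALT only, require more than 35% direct bilirubin or INR above 1.5, and set no ALP condition. Aligning the SAP with 8.3.6 does not unify all of these.

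These points stand, and they limit the size of the problem. They do not remove it. The Appendix 2 and Appendix 6 rules have the same inclusive cut-points, so they give no support for strict ones. The SAP's own example and Table 5–4 suggest that inclusive limits were meant, which favours correcting the sentence. A program written to the definition as it stands would still omit the Hy's Law flag at a tie.

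**Conclusion.** The concern holds and is minor. The SAP sentence is wrong as written: it departs from Protocol 8.3.6 on two cut-points, without a stated reason, and can only under-flag. What is lost is the programmed Hy's Law label for a participant exactly on a limit, and possibly the AESI label that depends on it. Few or no such cases are expected in about 30 participants. The primary PK endpoints, the treatment-emergent SAE endpoint, the stopping criteria and the 24-hour reporting duty do not change.

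The mismatch itself rests on the current text of both documents and needs no assumption. Only the statement that ties are uncommon relies on the assumed units and ULN ranges.

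**What to change.** In SAP 5.5.1.5.2, change the transaminase condition to ≥3 x ULN and the bilirubin condition to ≥2 x ULN. Keep ALP <2 x ULN and the same-visit requirement. Leave the protocol's clause on alternative explanations to medical review. No other flag and no protocol change is needed.

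The cost is two inequality signs in one sentence and the same condition in the listing program. AST, ALT, ALP and total bilirubin are already in the chemistry panel of Protocol Appendix 2, so no new data are needed. SAP section 1 requires an amendment when analysis definitions are modified, so the change can go in with any other SAP correction.

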**Table 5–3 Definitions of Markedly Abnormal Hematology Values**

Parameter (SI units)	Markedly Abnormal Definition	
	Low	High
Hemoglobin (g/L)	< LLN AND decrease from Baseline>20	N/A
Hemoglobin (g/L)	<80	N/A
Leukocytes (total x 1000)	<2.0	N/A
Lymphocytes (x 1000)	<0.5	N/A
Neutrophils (x 1000)	<1.0	N/A
Platelets (x 1000)	<50	N/A

N/A = Not Applicable

**Table 5–4 Definitions of Markedly Abnormal Biochemistry Values**

Parameter (SI units)	Markedly Abnormal Definition	
	Low	High
Alkaline Phosphatase	N/A	>3 x ULN
ALT	N/A	>3 x ULN
AST	N/A	>3 x ULN
Calcium (mmol/L)	<1.75	>3.125
CPK	N/A	>4 x ULN
Creatinine	N/A	>1.8 x ULN
Glucose (mmol/L)	<2.22	>13.89
Potassium (mmol/L)	<3.0	>6.4
Sodium (mmol/L)	<125	N/A
Total bilirubin	N/A	≥2 x ULN
Uric acid	N/A	≥3 x ULN

N/A = Not Applicable

Unscheduled visit and duplicate measurement will be handled in [Section 6.1.6.1](#) and baseline definition will be described in [Section 5.1.1.1.5](#).

### 5.5.1.5.3 Individual Participant Changes of Laboratory Values

For selected laboratory variables that are identified in [Section 5.5.1.5.2](#), the change in category from Baseline will be presented in shift tables at each post-Baseline assessment.

## 5.6 (Other) Safety Analyses

Other safety will be assessed using the SS. All safety endpoints will be analyzed using descriptive statistics. Safety summaries will include presentations of extent of exposure, and additional safety assessments including ECG and physical examination. For safety analysis, unscheduled visit and duplicate measurement will be handled in [Section 6.1.6.1](#) and baseline definition will be described in [Section 5.1.1.1.5](#).

### 5.6.1 Extent of Exposure

The number of injections, total doses received, and total duration of exposure will be summarized for SS with continuous statistics (eg, mean, std, median).

Duration of exposure to study medication will be calculated as:

- Date of last administration of study medication – date of first administration + 14 days

Time at risk (days) will be calculated as:

- Date of last administration of study medication – date of first administration + 70 days.

In addition, all IMP administration details (including date/time of administration, dose), where to perform injection (home or study site), who to perform the injection (study participant or site personnel), injection site (arm, abdomen or thigh), side of body (left or right), volume, injection speed (fastest-8 seconds, fast-11 seconds, slow-14 seconds and slowest-17 seconds) will be listed using the SS. All dosing records including self-injection at Week 14, 16, 20 and 22 with no specific visit label will also be listed and considered into exposure summary.

#### 5.6.1.1 Electrocardiograms

Standard 12-lead ECG recordings will be taken with the participant resting in the supine position for at least 5 minutes and will be presented in SS.

#### 5.6.1.2 Electrocardiogram Values Over Time

As ECG is only collected at Screening visit based on schedule of activities.

The following variables will be reported:

- Heart rate
- RR interval
- PR interval
- QRS duration
- QT interval
- QT interval corrected for heart rate (Bazett's formula)

Measured values will be summarized for each variable for all study participants at screening visit.

Electrocardiogram findings will be listed separately.

#### **5.6.1.2.1 Individual Participant of Electrocardiograms Values**

The results of all ECG variables will be reported in the by-participant listings. The listing will be presented for ASP at screening visit. All participants who may have clinically significant electrocardiogram (ECT) abnormalities at screening will be presented.

### **5.6.2 Additional Safety Assessments**

#### **5.6.2.1 Other safety endpoint(s)**

##### **5.6.2.1.1 Physical examination**

Study participants with abnormalities in the physical examination will be listed including details of the abnormality and based on SS.

##### **5.6.2.1.2 Additional Laboratory Tests**

In this study, details of all pregnancies in female participants will be collected after the start of study treatment and until SFU Visit and listed in additional laboratory test. In addition, other screening tests results also include serum or urine alcohol and drug screen and will be listed for SS.

### **5.7 Other Analyses**

#### **5.7.1 Other endpoints and/or parameters**

##### **5.7.1.1 Pharmacokinetics**

Pharmacokinetic samples will be tested using the ECLIA method. All PK assessments will be evaluated as described in the Section 5.3.

##### **5.7.1.2 Pharmacodynamics**

Pharmacodynamic parameters will not be evaluated in this study.

##### **5.7.1.3 Genomics**

Genomics will not be evaluated in this study.

##### **5.7.1.4 Tuberculosis screening (IGRA) and Tuberculosis Questionnaire**

TB test data at Screening period and TB questionnaire at Week 12 and Week 24 be listed on the SS.

##### **5.7.1.5 COVID-19 Impact**

For study participants impacted by the COVID-19 global pandemic, data was collected on a separate eCRF. This form was collected for study visits that were affected by COVID-19, and it collected how the visits were impacted by the pandemic (e.g., performed out of window, done by telephone instead of on-site, not done, etc).

Based on how the visit was affected by the global pandemic, all visits will have following impact categories indicating how the visit was performed:

- Visit not done
- Visit performed out of window
- Home visit
- Missed study drug
- Administration/dispensation
- Temporary discontinuation of study drug
- Termination of study participation
- Other (if other, specify the details)

Additionally, for visits that are affected by COVID-19, all assessments that are missing will be flagged as missing due to COVID-19. Further, the specific reason of missing data will be captured as the following flags:

- Confirmed COVID-19 infection
- Suspected COVID-19 infection
- General circumstances around COVID-19 without infection
- Other

A summary of number and percentage of study participants with COVID-19 impact for all study participants and visit will be provided for the ASP.

A by-site, participant and visit listing of COVID-19 related protocol deviations will be provided including impacted visit and date of impacted visit.

## **5.8 Subgroup analyses**

Not applicable.

## **5.9 Interim Analyses**

No interim analysis is planned.

## **5.10 Data Monitoring Committee (DMC) or Other Review Board**

No data monitoring is planned.

# **6 SUPPORTING DOCUMENTATION**

## **6.1 Appendix 1 Non-key analysis specifications**

### **6.1.1 Baseline characteristics and demographics**

A by- participant listing of Baseline demographics will be presented for ASP. This will include the participant number, year of birth (if available), age (in years), country, sex, race, ethnicity, height

(in cm), weight (in kg at screening and at pre-dose) and body mass index (BMI). The age will be directly entered into the study database and will not be re-calculated for the statistical analysis. Concomitant MTX use will also be presented and include:

- With MTX use at screening
- Without MTX use at screening

As study participants may take concomitant methotrexate (MTX) during the study, a minimum of 8 study participants must be enrolled who are not on concurrent administration of MTX, so at least 8 study participants will be expected for subgroup of “without MTX use at screening”. In addition, the non-MTX study participant may start to take MTX after Week 12, Day 84 where a study participant not on MTX at screening. The MTX user subgroup above will be only based on MTX status at screening status, even if a study participant enrolled to study as non -MTX user but then used an MTX after Week 12, this study participant will be still classified into “without MTX use at screening”.

All demographic characteristics obtained at the Screening visit and at pre-dose visit for weight will be summarized for the SS and the ASP (apart from the date of birth).

Body mass index in kg/m^2 is calculated based on the height (in m) and the weight (in kg) using the following formula:

$$\text{BMI (kg/m}^2\text{)} = \text{weight (kg)} / [\text{height (m)}]^2$$

The BMI will be reported to 1 decimal place.

For the EudraCT reporting, the age categories will include:

- 18 to <65 years
- 65 to <85 years
- ≥85 years

For the clinicaltrials.gov reporting, the age categories will include:

- ≤18 years
- 19 to <65 years
- ≥65 years

Childbearing potential will be listed by all study participants screened.

### 6.1.2 Protocol deviations

Important protocol deviations (IPDs) will be identified and classified by the deviation types identified in the IPD document.

Important protocol deviations will be summarized for all study participants (ASP) to include number and percentage of participants with

- 1) No important protocol deviations
- 2) At least one protocol deviation and the
  - Inclusion criteria deviation
  - Exclusion criteria deviation

- Withdrawal criteria deviation
- Prohibited concomitant medication use
- Incorrect treatment or dose
- Treatment non-compliance

3) Exclusion from the PKS (and all categories in item 2 above).

A by-participant listing of important protocol deviations will be provided using the SS.

A by-site participant listing of COVID-19 related important protocol deviations will be provided using the SS.

### 6.1.3 Medical history

Medical history will be listed and summarized for the SS and will include the MedDRA version 23.1 system organ class (SOC) and preferred term (PT). Procedure history will be listed separately from the medical history including date of procedure and relationship with RA based on the SS. Similarly, concomitant medical procedure will be also listed separately including date of procedure and procedure primarily relationship based on the SS. For study participants with DILI events, hepatic events supplemental medical history and relevant data (potentially hepato-toxic medication, symptoms of hepatitis and symptoms of hypersensitivity) for study participants with suspected DILI event will be listed with liver function laboratory results.

